#### **4.2.2 Exclusion Criteria**

**Target Disease Exceptions** Patients with acute nephritis requiring induction therapy, CNS lupus (except chorea, cranial neuropathy, and resolving optic neuritis) or any lupus condition requiring cyclophosphamide, biologics, or IV bolus steroids of  $\geq 500$  mg.

##### **1) Medical History and Concurrent Diseases**

- a. Subjects who are incapable of understanding or completing study-related assessments.
- b. Subjects with any condition, whether or not related to SLE, which, in the opinion of the investigator, might place a subject at unacceptable risk for participation in the study.
- c. Subjects with a history of cancer in the last 5 years, other than non-melanoma skin cell cancers cured by local resection or carcinoma in situ.
- d. Subjects who currently abuse drugs or alcohol.
- e. Subjects with herpes zoster or cytomegalovirus (CMV) that resolved less than 2 months before the informed consent document was signed.
- f. Subjects who have received any live vaccines within 3 months of the anticipated first dose of study medication.
- g. Subjects with any serious bacterial infection within the last 3 months, unless treated and resolved with antibiotics, or any chronic bacterial infection (eg, chronic pyelonephritis, osteomyelitis, or bronchiectasis).
- h. Subjects at risk for tuberculosis (TB). Subjects with active TB within 3 years, even if treated; history of active TB  $> 3$  years ago, unless documented prior anti-TB treatment appropriate in duration and type; current known or suspected active TB; and latent TB not successfully treated ( $\geq 4$  weeks at baseline).

##### **2) Physical and Laboratory Test Findings**

- a) Subjects must not be known to be positive for hepatitis B surface antigen.
- b) Subjects who are known to be positive for hepatitis C antibody may participate if the presence of hepatitis C virus can be excluded by polymerase chain reaction or recombinant immunoblot assay at screening.
- c) Subjects with any of the following laboratory values
  - i) Acute hemolytic anemia with hemoglobin  $< 7.0$  g/dL or known change in Hg by  $2.0$  g/dL within the last four months unless due to SLE and stable for the past month
  - ii) WBC  $< 2500/\text{mm}^3$  ( $< 2.5 \times 10^9/\text{L}$ ) unless due to chronic lupus activity and stable for the past month
  - iii) Platelets  $< 40,000/\text{mm}^3$  ( $< 3 \times 10^9/\text{L}$ ) (If less than 100,000 must have been stable (within a range of  $10,000/\text{mm}^3$ ) either by historical testing of known chronic thrombocytopenic patients within two months of screening or in two tests during the screening period at least one week apart.
  - iv) Serum creatinine  $> 2$  times the ULN
  - v) Serum ALT or AST  $> 2.5$  times the ULN
- d) Any other laboratory test results that, in the opinion of the investigator, might place a subject at unacceptable risk for participation in the study.

**4) Allergies and Adverse Drug Reactions:** Known allergy or adverse sensitivity to any components of the study agent or carrier.

**5) Sex and Reproductive Status:** See Section on WOCBP (Section 4.2.1, item # 3.)

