	
completing study-related assessments.
 
3) Subjects with any condition, whether or not related to SLE, which, in the opinion of the investigator, might place a subject at unacceptable risk for participation in the study.
 
4) Subjects with a history of cancer in the last 5 years, other than non-melanoma skin cell cancers cured by local resection or carcinoma in situ.
 
5) Subjects who currently abuse drugs or alcohol.
 
6) Subjects with acute herpes zoster or cytomegalovirus (CMV) within 2 months of screening.
 
7) Subjects who have received any live vaccines within 3 months of first dose.
 
8) Subjects with any serious bacterial infection within the last 3 months, unless treated and resolved with antibiotics, or any chronic bacterial infection (eg, chronic pyelonephritis, osteomyelitis, or bronchiectasis).
 
9) Subjects at risk for tuberculosis (TB).
 
10) Subjects known to be positive for hepatitis B surface antigen or hepatitis C unless negative by PCR or RIBA
 
11) Acute hemolytic anemia with hemoglobin < 7.0 g/dL or known change in Hg by 2.0 g/dL within four months
 
12) WBC < 2500/mm^3 (< 3 x 10^9/L) unless due to chronic stable lupus activity
 
13) Platelets < 40,000/mm^3 (< 3 x 10^9/L) (If less than 100,000 must have been stable (within a range of 10,000/mm^3 ) within two months of screening or in two tests during the screening period.
 
14) Serum creatinine > 2 times the ULN
 
15) Serum ALT or AST > 2.5 times the ULN
 
16) Any other laboratory test results that, in the opinion of the investigator, might place a subject at unacceptable risk for participation in the study.
 
17) Known allergy/sensitivity to the study agent or carrier.
 
18) Treatment with investigational drug within 28 days (or 5 terminal half-lives) of the Day 1 dose.
 
19) Cyclophosphamide within 3 months of Day 1 or bolus IV steroids >/=500 mg within 1 month
 
20) Prednisone > 20 mg qd after the screening visit

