**Other Exclusion Criteria**

- Prisoners or subjects who are involuntarily incarcerated.
- Subjects who are compulsorily detained for treatment of either a psychiatric or physical (eg, infectious disease) illness.

Eligibility criteria for this study have been carefully considered to ensure the safety of the study subjects and to ensure that the results of the study can be used. It is imperative that subjects fully meet all eligibility criteria.

**4.2.3 Discontinuation of Subjects from Treatment:** Subjects MUST discontinue investigational product for any of the following reasons:

- Withdrawal of informed consent (subject's decision to withdraw for any reason).
- Any clinical adverse event, laboratory abnormality, or intercurrent illness which, in the opinion of the investigator, indicates that continued participation in the study is not in the best interest of the subject.
- Pregnancy: WOCBP will be instructed to contact the investigator or study staff if they suspect they might be pregnant (eg, missed/late menstrual period) at any time during study. Urine pregnancy tests will be performed at each monthly visit as well. The investigator will immediately notify BMS if a study subject becomes pregnant.
- Loss of ability to freely provide consent through imprisonment or involuntary incarceration for treatment of either a psychiatric or physical illness.

All subjects who discontinue should comply with protocol-specified follow-up procedures outlined in Section 6. This will entail monthly visits if subjects discontinue treatment prior to month 6, and then a visit 2 months after withdrawal and an additional visit four months after withdrawal at which safety and efficacy evaluations will be performed the same as the Month 6 visit. The only exception to this is when a subject withdraws consent or loses the ability to consent freely

(ie, is imprisoned or involuntarily incarcerated for the treatment of either a psychiatric or physical illness). If a subject withdraws before completing the study, the reason for withdrawal must be

documented appropriately. The second six months of open label therapy are optional. Patients will be determined to complete the protocol if they complete Month 6 and two follow up visits. Patients will be considered evaluable for the primary endpoint if they complete Month 6. Patients lost to follow up before Month 6 will be considered non-responders.

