**THROMBOCYTOPENIA:**

*Definition: <100,000 platelets/mm^3.*

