**LEUKOPENIA:**

*Definition: <3,000 white blood cells/mm^3. Exclude drug causes.*

This is exactly as described, WBC <3,000/mm^3. The presence of an absolute lymphopenia does not count in the SLEDAI. A note of caution, do not confuse this WBC with that used to satisfy the ACR criteria for SLE which is WBC <3,500/mm^3.

With regard to current use of possible offending drugs, the following guidelines are to be considered:

1. The nadir after cyclophosphamide, i.e., low WBC at 10 days after receiving cyclophosphamide in a patient known to have a WBC  $\geq$  3,000 at the time of receiving cyclophosphamide should not be counted.
2. Do not score leukopenia appearing after initiation of a new medication known to be associated with leukopenia, such as azathioprine or sulfa drugs. If the patient develops a WBC <3000 while taking drugs which may cause leukopenia, score this only if the dosage of medication is unchanged since the last WBC determination.

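### Platelet exclusion gives 3 × 10^9/L as the equivalent of 40,000/mm3 in the Synopsis and Section 4.2.2, and the Synopsis WBC exclusion gives 3 instead of 2.5 × 10^9/L

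*Combined protocol and SAP*

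**What the plan says.** Two haematology exclusions are each given in two units, once in the Synopsis and once in the full criteria.

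- **Platelets, Synopsis, exclusion 13:** "40,000/mm 3 (< 3 x 10 9 /L) (If less than 100,000 must have been stable".
- **Platelets, Section 4.2.2, item 2(c)(iii):** the same limit of 40,000/mm3, with the SI equivalent again printed as "3 \times 10^9/\text{L}$ ) (If less than 100,000 must have been stable". Both places add that a count under 100,000 must have stayed within a range of 10,000/mm3.
- **WBC, Synopsis, exclusion 12:** a limit of 2500/mm3, with the equivalent printed as "3 x 10 9 /L) unless due to chronic stable lupus activity".
- **WBC, Section 4.2.2, item 2(c)(ii):** the same limit of 2500/mm3, with the equivalent printed as "2.5 \times 10^9/\text{L}$ ) unless due to chronic lupus activity and stable for the past month".

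Section 4.2.2 closes its criteria with the statement "It is imperative that subjects fully meet all eligibility criteria".

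**The concern.** The SI figure should restate the per-mm3 limit in other units. In three of the four lines it does not, so those lines carry two different thresholds for the same test.

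The platelet line matters more. It is a safety criterion in a trial that withdraws background immune suppressants, and the error also stands in the full eligibility section. Site staff whose laboratory reports in 10^9/L would look to the figure in brackets. Read alone, that figure lets in counts that the protocol's own scales class as severe. In Appendix 2, lupus-related platelets below 25 × 10^9/L score haematological Category A, which is defined as severe disease. The revised flare index in Appendix 1 rates counts below 30,000 as severe.

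For audit, a patient at 35 × 10^9/L is excluded by the first figure and, subject to the stability rule, admissible by the second. Section 10.1 requires all deviations to be reported to the IRB and DSMB, so whether such a patient is a deviation should not depend on which figure is read.

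**Working it through.** **Conversion.** 1 L = 10^6 mm3, so a count in 10^9/L = (count per mm3) × 10^6 ÷ 10^9 = (count per mm3) ÷ 1000.

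**Check of the factor on the protocol's own pairs (Appendix 1).**
- Thrombocytopenia: the SLEDAI table gives 100 × 10^9/L and the scoring guideline gives "<100,000 platelets/mm"3. 100,000 ÷ 1000 = 100. They agree.
- Leukopenia: the table gives 3 × 10^9/L and the guideline says "This is exactly as described, WBC <3,000/mm"3. 3,000 ÷ 1000 = 3. They agree.

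**The four exclusion lines.**

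| Line | Limit per mm3 | Correct (10^9/L) | Printed (10^9/L) | Printed value per mm3 | Match |
|---|---|---|---|---|---|
| Platelets, Synopsis 13 | 40,000 | 40 | 3 | 3,000 | No |
| Platelets, 4.2.2 item 2(c)(iii) | 40,000 | 40 | 3 | 3,000 | No |
| WBC, Synopsis 12 | 2500 | 2.5 | 3 | 3,000 | No |
| WBC, 4.2.2 item 2(c)(ii) | 2500 | 2.5 | 2.5 | 2500 | Yes |

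**Size of the discrepancies.**
- Platelets: 40 ÷ 3 = 13.3. The two printed limits disagree for counts from 3 to below 40 × 10^9/L.
- WBC, Synopsis only: 3 ÷ 2.5 = 1.2, so the printed SI limit is 20% above the stated one. The limits disagree over 3.0 − 2.5 = 0.5 × 10^9/L, that is from 2.5 to below 3.0, and only for patients outside the chronic stable lupus exception. In that range the SI figure excludes more patients.

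**Which platelet figure is meant.**
- The per-mm3 limits come first and are identical in the Synopsis and Section 4.2.2.
- The stability band of 10,000/mm3 is 10 × 10^9/L, and 10 ÷ 3 = 3.3, so the band would be more than three times a floor of 3 × 10^9/L. It fits a floor of 40 × 10^9/L.
- The printed 3 equals the SLEDAI leukopenia cut-off, so it may be a white-cell value carried over. The documents do not say, and nothing here depends on it.

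**Could it be a reading error from the PDF?** This is unlikely. The wrong platelet figure stands in two separately typeset places, and in Section 4.2.2 the WBC conversion directly above it reads correctly.

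**The case against.** The strongest reply is that this is an editorial slip in a bracketed gloss. The per-mm3 limits agree throughout, the rest of the platelet rule makes sense only around 40,000/mm3, and anyone reading the whole line would apply that limit. Other text also protects patients:

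- Section 4.2.2 lets the investigator exclude anyone at unacceptable risk, on medical or on laboratory grounds.
- Section 4.1 requires patients to be stable enough for a design with withdrawal.
- Raters must pass testing on BILAG 2004, whose platelet bands are in SI units (A below 25, B 25–49, C 50–149 × 10^9/L), so a floor of 3 would look wrong to them.
- Much severe thrombocytopenia would be caught by the exclusions for disease needing cyclophosphamide, biologics or IV bolus steroids of 500 mg or more, or for prednisone above 20 mg at screening.
- The WBC slip is in the Synopsis only and is on the strict side.

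Most of this stands, and it makes the practical risk small. The factor of 13.3 measures the misprint. It does not estimate how many patients might be wrongly enrolled.

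The reply does not remove the error. The judgement-based safeguards are discretionary and do not replace a numeric limit. The overlap with the severe-disease exclusions is incomplete: it bears mainly on counts below 25 × 10^9/L, while counts from 25 to below 40 score BILAG B and are still inside the conflict range. That the intended value can be worked out is a reason to expect little harm, but the criteria should not need working out.

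**Conclusion.** The point holds. Three of the four SI equivalents are wrong: platelets in the Synopsis and in Section 4.2.2 (3 printed, 40 × 10^9/L correct), and WBC in the Synopsis (3 printed, 2.5 × 10^9/L correct). The arithmetic is exact, and the protocol's own conversions in Appendix 1 confirm it.

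The only assumption is that the per-mm3 values are the intended thresholds. The internal evidence for this is strong, but it is for the clinical team to confirm.

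The effect is limited to the wording of eligibility and to audit against it. The sample size, power, alpha and primary endpoint are unaffected. It is worth correcting because the platelet limit is an operative safety threshold that is wrong by more than tenfold in the full criteria.

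**What to change.** 1. Have the clinical team confirm 40,000/mm3 (platelets) and 2500/mm3 (WBC) as the intended limits.
2. In Synopsis exclusion 13 and Section 4.2.2 item 2(c)(iii), change the platelet equivalent to < 40 × 10^9/L.
3. In Synopsis exclusion 12, change the WBC equivalent to < 2.5 × 10^9/L, to match Section 4.2.2.

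The cost is three figures in the next amendment, with no change to design, sample size or analysis.

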**6) Prohibited Treatments and/or Therapies**

- a) Subjects who have at any time received treatment with any investigational drug within 28 days (or less than 5 terminal half-lives of elimination) of the Day 1 dose.
- b) Subjects who have received cyclophosphamide within 3 months of the Day 1 dose or bolus parenteral steroids  $\geq$  500 mg within 1 month of screening.
- c) Ongoing treatment (after the baseline visit) with immune suppressants (such as antimalarials, methotrexate, azathioprine, mycophenolate mofetil, leflunomide, calcineurin inhibitors or belimumab) after the baseline visit. These may be stopped or tapered as soon as informed consent procedures have been completed at the screening visit.
- d) Prednisone  $> 20$  mg po qd at the time of the screening visit (steroids will additionally be tapered during the study if possible at the discretion of the investigator). The exception to this are the protocol-allowed Depomedrol shots which will be used for rescue if needed. A total of 320 mg of intramuscular depomedrol can be given in increments of 40-160 mg at any time from the Screening Visit (after informed consent is signed and blood drawn) until the end of the Month 2 Visit (after blood drawn) If subjects remain on prednisone, no dose increases will be allowed during the study.

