## PROTOCOL SYNOPSIS

Protocol Title:	Clarification of Abatacept Effects in SLE with Integrated Biologic and Clinical Approaches (The ABC Study) The ABC Study:
Site Numbers/ Names:	Site 1: Oklahoma Medical Research Foundation
Research Hypothesis:	Abatacept is effective in lupus arthritis and this will be discernible in a small trial with robust endpoints which incorporates withdrawal of background immune suppressants
Study Schema: Drugs / Doses / Length of Treatment)	
 
1. Abatacept or placebo will be given in a 1:1 randomization subcutaneously q week for six months. Patients may elect to continue six more months on open label Abatacept.
 
2. Background Immune Suppressants will be withdrawn at any time between screening and the first dosing visit.
 
3. At or after screening, patients may elect 40-160 mg depomedrol shots prn not to exceed 320 mg total up to and including the Month 2 Visit (two months after the first dosing visit)
 
4. Additional steroids or immune suppressants, if necessary, will be allowed but the patient will be considered a non-responder on that basis
 
5. At the 3 month visit patients with significant clinical flare unresponsive to optional per protocol treatments may elect to receive open label Abatacept but will be considered non-responders in the primary endpoint at six months.
 

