## **Ethical Considerations:**

Integration of biologic discovery into clinical trials will generate data that might be used to help select more appropriate patient subsets for future trials and future treatment in clinic and to guide optimal dosing strategies. This is an ethical consideration since it could decrease the numbers of patients inappropriately exposed to a study medication in trials and in practice, and by allowing a better delineation of efficacy in the right population(s) this could also decrease the likelihood of widespread exposure in Phase III trials prior to acquiring sufficient data supporting potential efficacy.

The ethical basis of the current trial design has been debated widely in the lupus community. There is a realistic concern that withdrawal of background therapy will increase the risk of lupus flares and this trial design would be inappropriate for very ill patients such as those with active nephritis. However by decreasing the continued use of background immune suppressants which were obviously not working at the time of entry, by allowing steroid rescue and even restarting of meds as needed during the trial (defining such patients as non-responders) this design could be argued to be far more ethical than trials which legislate continuance of inadequate and potentially toxic background immune suppressant treatments for an entire year, with probable increase in risk for infections. In such protocols, patients who do not improve have only the choice of minimal rescue steroids or to drop out of the study, leading to unnecessary suffering which will not be required in this trial design. Finally, the concern about increasing flare risk should be somewhat alleviated by the results of the MMF, BOLD and Rontalizumab studies (all three of which have been completed using this trial design, and the latter presented at ACR 2012 (39)

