**Screening procedures:** At the screening visit, patients who are known to have 4 ACR classification criteria (1997 revised) for SLE who present with active arthritis (a minimum of 3 swollen and 3 tender joints) will be invited to undertake screening procedures unless an exclusionary criteria is already known. Screening procedures will begin with the informed consent process during which patients will review the complete informed consent information as approved by the IRB, which will include a full description of the study and the procedures involved, patients' rights and responsibilities, and alternative treatments that are available if the patient does not decide to participate in the study.

Subjects will have a chance to have their questions answered prior to making a decision. Once the informed consent procedures are completed, the following will be completed: medical history, physical examination, review of inclusion and exclusion criteria (some of which will require awaiting blood test results), EKG, PRO measures filled out by the participant (Lupus PRO and SF-36), and clinician measures (SLEDAI, BILAG 2004, CLASI, DIAL, PGA).

To the extent that a history and physical examination was already performed by one of the investigators that day in the course of routine medical care they will not need to be repeated. Screening blood tests will be drawn (maximum 160 cc) including baseline PK and PD samples, and arrangements will be made to contact the patient for the first dosing visit or (if is determined the subject is ineligible) a visit to discuss alternative care. Patients who donate blood at screening for PK and PD and who are later deemed ineligible for the trial will be told, as part of the informed consent process, that these samples may be used for various analyses. Patients retain the right to withdraw

permission for the use of their blood samples at any time. Screening procedures can be performed on the same day the informed consent is signed or any other time up to and including the baseline visit (the screening period) as long as full eligibility is established at the time of randomization.

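### Section 4.2.2 item 6(c) and synopsis item 2 allow study-driven stopping of immune suppressants before the screening laboratory results that could exclude the patient are known

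*Combined protocol and SAP*

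**What the plan says.** Two places set when background immune suppressants may be withdrawn. Section 4.2.2 item 6(c) bars them after the baseline visit and adds: "These may be stopped or tapered as soon as informed consent procedures have been completed at the screening visit". Synopsis, Study Schema item 2, states: "Background Immune Suppressants will be withdrawn at any time between screening and the first dosing visit". Section 4.1 fixes the other end of the window: the drug may be continued up to the day of the baseline visit itself.

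Eligibility runs on a different clock. The Section 4.1 screening procedures include "review of inclusion and exclusion criteria (some of which will require awaiting blood test results". They may be done on the day of consent; the alternative that the section gives is "any other time up to and including the baseline visit (the screening period) as long as full eligibility is established at the time of randomization". A patient found ineligible is offered "if is determined the subject is ineligible) a visit to discuss alternative care".

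The laboratory exclusions are in Section 4.2.2 under Physical and Laboratory Test Findings. They cover hemoglobin, white cells, platelets, creatinine, ALT/AST, any other result that the investigator considers unsafe, and exclusion of hepatitis C virus by PCR or immunoblot in patients known to be antibody-positive. Platelets below 100,000/mm³ without a suitable historical value need two screening tests at least one week apart. Section 6.1 places randomization within one month of screening.

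**The concern.** The stop is tied to consent, while the decision on whether the patient can enter is tied to laboratory results that come later. Nothing in item 6(c) or synopsis item 2 connects the two. A patient on, say, methotrexate or mycophenolate can sign consent, stop the drug for the study that day, and then fail on a creatinine or platelet result. That patient has taken on the flare risk of withdrawal, which the Ethical Considerations section acknowledges, with no prospect of being randomized.

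What is at stake is patient safety and consistency of procedure. Such a patient is never randomized and so never enters the intent-to-treat comparison.

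**Working it through.** The plan states no figure on this point, so the check sets the rules side by side and works out the intervals they allow.

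**Sequence the text allows**

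1. Day 0, screening visit: consent is completed. Study-driven stopping or tapering is allowed from here (item 6(c); synopsis item 2).
2. Day 0 or later: screening blood is drawn. Section 4.1 lets screening procedures fall on any day up to and including baseline.
3. Later still: results return and the laboratory exclusions can be applied.
4. By about one month: randomization (Section 6.1), the first point at which full eligibility must be established (Section 4.1).

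Step 1 can come before step 3, and no rule prevents it. The permissive reading is therefore correct.

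**Is an early stop ever required?** No. Item 6(c) is permissive, and Section 4.1 accepts a stop on the day of baseline. An investigator can already choose to wait for results.

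**Needless interval off therapy**, for a patient who stops on day 0 and fails on a laboratory result:

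interval = day the excluding result is known − day of stopping

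- Blood drawn at the screening visit, routine turnaround: a few days. Turnaround time is an assumption; the documents do not state it.
- Second platelet test needed: at least 7 days, from the one-week spacing in Section 4.2.2.
- Blood drawn close to baseline: up to about one month, from Sections 4.1 and 6.1. It could be longer only where screening is extended, as Section 6.3.2 allows after a suspicious cancer screen.

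**Effect of the fix on an eligible patient.** The taper window now runs from consent to baseline. Under the fix it would run from reviewed results to baseline. For a given patient, the window therefore shortens by the same interval: a few days, or at least 7 days with a platelet retest. If the blood were still drawn near baseline, almost no window would be left. This is why the fix also moves the draw to the screening visit.

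**How many patients?** Section 9 expects at least 70 screened and 60 randomized: 70 − 60 = 10, and 10/70 = 14.3% not randomized for any reason. This only sets the scale. Those affected are the subset who were taking an immune suppressant, stopped it early for the study, and then failed on a laboratory result not known beforehand. The documents give none of these three shares, so no count can be derived. Nor is 10 a firm ceiling, because Section 9 says at least 70 and the synopsis accrual goal is 60 completers.

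**The case against.** The strongest reply is that clinical judgement already covers this. Early stopping is optional. Section 4.1 keeps patients with a known exclusion from being invited to screen, and it requires the investigator to judge each patient stable enough for withdrawal. Most recruits come from the site's own lupus cohort (Section 9.4.1), which makes laboratory surprises less likely. All have active arthritis, and the Ethical Considerations section speaks of "background immune suppressants which were obviously not working at the time of entry", so therapy was probably due for review. Gating the stop narrows the taper for every patient on these drugs to protect very few. All of this stands as a reason to keep the point small. It does not change the order of events: judging that a patient can tolerate withdrawal is not the same as knowing that the patient can enter.

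Four stronger readings are tempting, and the documents do not support them.

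- *That the protocol recognized a safety gate and left it out of item 6(c).* Item 6(d) allows Depomedrol "at any time from the Screening Visit (after informed consent is signed and blood drawn", a condition that 6(c) lacks. The note to the Section 6.1 schedule explains it: screening pharmacokinetic, immunogenicity and pharmacodynamic samples must precede any steroid injection. It is a sampling rule, and the steroid can itself be given before any result is back.
- *That an ineligible patient loses the right to restart.* The ethics argument relies on "by allowing steroid rescue and even restarting of meds as needed during the trial", and Section 5.6.1 limits restarting. Those limits bind patients in the protocol. Nothing forbids a screen failure from resuming the drug.
- *That screen failures have no care path.* Section 4.1 gives them a visit on alternative care, where the previous drug would naturally be discussed. Depomedrol is available from screening, and Section 7.2.1 collects serious adverse events from consent, with provision to record a link to withdrawal of earlier therapy.
- *That about 10 patients are at risk.* That figure counts non-randomization for any reason.

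**Conclusion.** The point holds in limited form. Item 6(c) and synopsis item 2 allow, without requiring, study-driven withdrawal of immune suppressants before the exclusionary laboratory results are known, so a patient can give up therapy for a trial that is then closed to them. The number affected is unknown and probably very small. The needless interval is usually days, on the assumption of routine turnaround; the one-month case needs both a late blood draw and an early stop. No trial result changes.

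The absence of any wording about resuming the stopped drug is a matter of detail, since the alternative-care visit would ordinarily cover it. The consent text is not among the documents, so what patients are told about stopping early cannot be checked. This is an optional improvement, worth making because it is cheap.

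**What to change.** Draw the safety bloods at the screening visit, and amend item 6(c) and synopsis item 2 in substance as follows:

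> Study-driven stopping or tapering of immune suppressants may begin once the screening laboratory results have been reviewed and show no exclusion, including the second platelet test where one is needed. It must be complete on or before the baseline visit. Stopping a drug for clinical reasons unrelated to the study is not affected.

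As a wording clarification only, Section 4.1 could name resumption of prior therapy, where clinically appropriate, as an option at the existing alternative-care visit. It should not be automatic: Appendix 1 lists azathioprine among drugs associated with leukopenia, so some laboratory failures would call for a review of the drug in any case.

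Cost: a short text change in two places and no new visit or test, because the bloods, the contact before first dosing and the alternative-care visit are already planned. The optional taper window before baseline becomes shorter. Where too little of it remains, the drug is stopped at baseline, which Section 4.1 already accepts, or the baseline visit is put back.
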